11.1. Participant Completion

Practice Sites: A practice site will be considered as having completed the study after the caregiver of the last infant that was observed through EHR during the 18-month practice observation period has been contacted before that infant reaches 12 months of age.

Pediatric Clinicians: A pediatric clinician will be considered as having completed the study after having finished the last pediatric clinician survey, at the end of the study's 18-month practice observation period.

Infants: An infant will be considered as having completed the study after the last observations from her/his EHR record at 30 months of age are extracted.

Caregivers: A caregiver will be considered as having completed the study after participating in the study questionnaire and survey, when the child is 24 months of age.

11.2. Participant Stopping Rules and Withdrawal Criteria

Practice Sites:

1. A practice site may elect to withdraw from current or future study activities.
2. The investigator, with the NIAID medical monitor's approval, can terminate a practice site if it fails to fulfill its obligations in accordance to the iREACH protocol.

Pediatric Clinicians:

1. A pediatric clinician may withdraw consent from participating in surveys.
2. When pediatric clinician leaves the practice for any reason they will be withdrawn from the study.
3. The investigator, with the NIAID medical monitor's approval, can terminate a pediatric clinician from participating in study activities if the investigator believes that further participation compromises the integrity of the study.

Infants:

1. Because infant data are obtained through the EHR and are only observational, no stopping rules nor withdrawal criteria apply.

Caregivers:

1. A caregiver may elect to withdraw consent from all future study activities; in such case, the caregiver will not be contacted by study staff for any future surveys or questionnaires.

2. A caregiver is “lost to follow-up” and assumed withdrawn after five attempts to reestablish contact by study representatives have failed.
3. A caregiver is withdrawn if they die.
4. The investigator may opt to withdraw a caregiver if they believe further participation compromises the integrity of the study.
5. A caregiver may elect to withdraw their “notice of privacy agreement” with the practice of which their child is a patient. If this occurs and the study team is notified, the child’s EHR data will be deleted from the EHR database.

11.3. Participant Replacement

Practice Sites: In the event the number of participating randomized study sites falls below the target of 30, additional practices will be approached and, if agree to study participation, will complete a practice characteristic questionnaire that will document that practice inclusion and exclusion criteria are met.

Infants or Caregivers: Not applicable. There is no target number of infants that are to be observed via EHR data extraction in this study.

11.4. Follow-up after Early Study Withdrawal

Caregivers will have no follow-up if they choose to withdraw from participating in any remaining study surveys and questionnaires. The data that have already been obtained from these individuals will remain in the iREACH study database.

11.5. Study Stopping Rules

The study may be prematurely terminated for the following reasons:

If a breach of confidentiality as it pertains to infant personal health-related information occurs, the source of the breach will be investigated, identified, and resolved. If the source of the breach of confidentiality cannot be resolved, study will be placed on hold. If this stopping rule is met, the DSMB will be asked to review the circumstances under which breaches occurred and provide an opinion whether the study should be terminated or whether specific changes will need to be made in order for the study to resume.

If there is a change in PPA Guidelines that may affect study procedures and outcomes, the study will pause, and the study team will review implications and revise procedures as necessary.

12. Safety Monitoring and Reporting

12.1 Overview

This is an educational intervention trial with the subjects of the intervention being pediatric clinicians. The objective of the intervention is to improve the implementation of the PPA Guidelines, which are now considered standard of care in the USA. As such, no adverse events (AEs) in the pediatric clinicians are expected or will be recorded.

It is possible that, as a result of implementing the standard of care PPA Guidelines, some infants under the care of the study’s pediatric clinicians may experience reactions to the introduction and/or later use of peanut-containing food. These reactions will not be recorded as AEs because a) such reactions may or may not be captured by the clinician in the EHR and the study has no control over this factor, b) since the study team is blinded as to the identity of the child that may experience such a reaction, study staff has no means of

contacting the child's caregiver and obtaining any information about the reaction to allow appropriate grading, attribution and follow-up.

When the child reaches 12 months of age, and if the caregiver consents to participation in the survey, information on whether peanut-containing food was tolerated after early introduction and whether any allergic reactions occurred will be obtained by the study staff through a) the caregiver survey and b) linking the child's information extracted from the EHR to the caregiver's survey. At that stage of the study, immediate reactions to early introduction of peanut-containing foods or later reactions, after peanut-containing foods have been introduced into the child's diet, will be captured as a study outcome, but not as AEs, and reported as such to NIAID and to the Institutional Review Board (IRB) and the Data Monitoring Safety Board (DSMB) with routine reporting, in accordance with applicable regulations.

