8.2.2. EHR Data Extraction

Data collection will take place at both the practice network (e.g., Lurie Community Connect, Peoria area-OSF and Unity Point, Alliance Chicago) or practice level for inclusion in the EHR study database.

Each practice will have an information technology analyst responsible for facilitating data extraction at the practice level. Data from participating practices' EHRs will be extracted on a weekly basis through an automated process established by Lurie Children's Data Coordinating Center team (DCC) and sent to DCC via a secure file transfer protocol (SFTP). Practices will be provided a data dictionary and natural language processing code to identify the appropriate elements and visits/services to extract. DCC will develop Extract Transform Load (ETL) scripts on behalf of the practice network (with the appropriate approvals from the practices). The ETL

scripts will be run weekly so that each week the Lurie Children's DCC data manager will have a complete EHR-based data file for reporting compliance and participation metrics. The weekly file will also be used to identify new providers hired by the practices who may need training in the intervention.

The EHR study database will include data from each of the following types of health care encounters documented in the EHR:

1. 4-month WCC
2. 6-month WCC
3. 9-month WCC
4. 12-month WCC
5. 15-month WCC
6. 18-month WCC
7. 24-month WCC
8. Additional sick visits until 30 months of age
9. Allergy visits until 30 months of age
10. Emergency department visits until 30 months of age

Table 8.2 presents the data elements that will be collected in the EHR study database. Partial PHI including the full date of birth, patient zip code, and date of service will be included.

Table 8.2 EHR Data Elements

| EHR Activities | Data Collected |
|---|--|
| Infant characteristics | Gender, race, ethnicity, date of birth, height and weight over time, patient zip code at 4- month WCC, patient zip code at 6-month WCC, health insurance type at 4-month WCC, health insurance type at 6-month WCC |
| Problem list | Type of problem, date problem entered, date problem resolved |
| Medications list | Medications ordered, order date |
| Primary care visits (well or sick) | Date of service, peanut product introduction recommendation (NLP based), severe eczema (NLP based), eczema ICD-10 code, food allergy ICD-10 codes, date of allergy referral, CDS-specific fields (intervention arm only) |

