| Allergy visits | Date of service, peanut product introduction recommendation (NLP based), severe eczema (NLP based), food allergy ICD-10 codes. |
| Peanut testing | Date of test, type of test (peanut sIgE or peanut skin prick test), test result |
| Emergency Department visits | Date of ED visit, food allergy or anaphylaxis ICD-10 codes |

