12.8.2 DSMB Review

12.8.2.1 Planned DSMB Reviews

The Data and Safety Monitoring Board (DSMB) shall review the progress of the study and any available safety information at least yearly during planned DSMB Data Review Meetings. Data for the planned safety reviews will include, at a minimum, a listing of all reported unanticipated problems.

12.8.2.2 *Ad hoc* DSMB Reviews

In addition to the pre-scheduled data reviews, the DSMB may be called upon for ad hoc reviews. The DSMB will review any event that potentially impacts safety at the request of the Principal Investigator or DAIT/NIAID. After review of the data, the DSMB will make recommendations regarding study conduct and/or continuation.

12.8.2.2.1 Temporary Study Suspension of <enrollment/drug dosing or both> for *ad hoc* DSMB Safety Review

If an *ad hoc* safety review is triggered, the DAIT/NIAID will decide whether any aspects of the study should be temporarily suspended before an *ad hoc* DSMB review.

13. Statistical Considerations and Analytical Plan

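### Coded emergency-department visits are extracted weekly in both arms, but the plan does not require them to reach the DSMB or reaction counts to be shown by arm

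*Combined protocol and SAP*

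**What the plan says.** **Recording of reactions (section 12.1).** The protocol accepts that infants may react to peanut when the guidelines are followed, and states: "These reactions will not be recorded as AEs because" of two things. The first is that "such reactions may or may not be captured by the clinician in the EHR and the study has no control over this factor". The second begins "since the study team is blinded as to the identity of the child that may experience such a reaction" and concludes that staff cannot reach the caregiver, and so have no means of "obtaining any information about the reaction to allow appropriate grading, attribution and follow-up".

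**Reporting of reactions (section 12.1).** When the child is 12 months old, and "if the caregiver consents to participation in the survey", reactions found by the survey and the linked health record become a study outcome. They then go to NIAID, the IRB and the DSMB in routine reports.

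**Data already extracted (section 8.2.2).** The study database includes "Emergency department visits until 30 months of age". Table 8.2 gives the elements as "Date of ED visit, food allergy or anaphylaxis ICD-10 codes". Extraction is automated and weekly. The stated uses of the weekly file are compliance and participation metrics and spotting newly hired clinicians. Section 4.2 notes that an infant's data can be included without caregiver consent.

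**Oversight (section 12.8).** The DSMB meets at least yearly to review progress and whatever safety information is available. On content: "Data for the planned safety reviews will include, at a minimum, a listing of all reported unanticipated problems". Medical Monitor reports (12.8.1) compile unanticipated problems, and interim safety analysis (13.5.2) is marked not applicable.

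**Final analysis (section 13.4.6).** Reactions to first and to later peanut exposure are to be counted for every child in the infant sample, from health records and surveys. No split by arm is stated.

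**The concern.** The intervention encourages clinicians to recommend early peanut feeding, and the protocol itself foresees some reactions. The only route to the DSMB that it spells out for those reactions is late and limited to consenting families. A faster and wider, if cruder, source sits in the weekly extract with no safety use assigned to it. If severe reactions differed between arms during the 18-month observation period, nothing in the plan obliges anyone to tabulate the data that could show it. At the end of the trial, reaction counts pooled over arms would say little about whether the intervention changed them.

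**Working it through.** The plan states no figure on this point, so the check sets the sections side by side and adds simple arithmetic for scale.

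1. **Do the reasons in section 12.1 rule out a count?** The second reason concerns grading, attribution and follow-up of an individual child. A count by arm needs none of these: arm is fixed by practice (section 3.2), so neither the child's identity nor contact with the caregiver is required. The first reason says capture is uncertain, which limits how a count is read but does not prevent one.

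2. **Does the unanticipated-problem route cover it?** Section 12.7 requires an event to be unexpected in nature, severity or frequency, as well as related and suggestive of greater risk. Peanut reactions are foreseen in nature by section 12.1. An unexpected frequency can be seen only if someone tabulates it.

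3. **Coverage.** Expected infants (section 13.7): 500 + 10,000 = 10,500. The proportion r whose caregivers consent to the survey and to linkage is not given, and section 8.1 lets a caregiver answer without linking. Infants outside the route = 10,500 × (1 − r), with r assumed:
   - r = 30%: 10,500 × 0.70 = 7,350
   - r = 50%: 10,500 × 0.50 = 5,250
   - r = 70%: 10,500 × 0.30 = 3,150

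4. **Delay.** For a reaction at 4 to 7 months of age, the wait to the 12-month survey is 12 − 7 = 5 to 12 − 4 = 8 months. A DSMB that meets only yearly can add up to about 12 months, but that wait applies to either source. The gain from the extract is therefore the 5 to 8 months, plus the wider coverage in step 3.

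5. **Infants surveyed after observation ends.** Assume even accrual over 18 months. An infant first seen at 4 months of age turns 12 months old 8 months later, so those seen after month 10 do so after observation ends: 8/18 = 44%. For infants first seen at 6 months of age, the cut is month 12: 6/18 = 33%.

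6. **Internal consistency.** Section 12.1 limits reaction data to consenting families. Section 13.4.6 counts reactions for all children in the infant sample. The two do not describe the same set of infants.

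7. **Display by arm.** The paragraph after the reaction counts in section 13.4.6 asks for questionnaire summaries overall and by arm. The reaction paragraph does not.

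**The case against.** Three stronger readings are tempting, and the documents support none of them.

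- A reader might infer that reactions are kept out of safety reporting altogether. Section 12.1 keeps them out of adverse-event recording only, and sends them to NIAID, the IRB and the DSMB as a study outcome.
- A reader might infer that a rise in severe reactions could not reach the DSMB. Section 12.8.2 sets a floor, not a ceiling, has the board review whatever safety information is available, and allows ad hoc reviews. Emergency-department data are permitted; they are simply not required.
- A reader might infer that the protocol calls reaction data unobtainable and promises a safety benefit that it then leaves untested. The first reason in section 12.1 says only that capture is uncertain. Section 5.5 lists fewer home reactions as something that may follow if adherence improves, and it is not among the objectives in section 2.

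The case against acting also has substance. A coded visit supplies no grade or attribution. The codes are not stated to be peanut-specific. Visits outside the participating health records may be missed. The intervention prompts risk triage, testing and referral, and charting of tolerance at 9 and 12 months (section 6.1.1), while control records are left unmodified (section 3.2). Recognition and coding of allergy could therefore rise in one arm without any rise in reactions. The protocol also regards the guidelines as standard of care and sees no added risk to infants from study procedures (section 5.4).

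These limits stand, and they make any comparison descriptive. They do not explain why data already held should go untabulated.

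**Conclusion.** The point holds in a limited form. Coded emergency-department visits are extracted weekly in both arms without a consent condition, no section requires them to reach the DSMB, and the final reaction counts have no stated split by arm. The reporting route that does exist begins at 12 months of age and depends on consent. Under the assumed 30% to 70% rate it leaves out about 7,350 to 3,150 of 10,500 infants, and it adds 5 to 8 months for a reaction at 4 to 7 months of age.

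The sizes rest on the assumed consent-and-link rate and on expected enrolment. They count infants, not events, because the documents give no reaction rate, and they do not imply complete capture of emergency visits. The primary adherence analysis is unaffected. This is an inexpensive improvement to oversight, worth making.

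**What to change.** - **Section 12.8.2:** add to each planned DSMB report the number of infants with an anaphylaxis- or food-allergy-coded emergency visit, by arm and risk stratum, with the number of infants under follow-up as denominator. Say in section 13.5.2 that the table is descriptive monitoring and not a formal test.
- **Section 13.4.6:** report the two reaction counts and the coded-visit count by arm.
- **Sections 12.1 and 13.4.6:** reconcile which infants contribute reaction data, consenting families or all children, and from which source.
- **With every table:** state that the codes may not be peanut-specific, that visits outside the participating records may be missed, and that the intervention's prompts and testing may change coding in one arm.

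The cost is one table per DSMB report and a few sentences of text. It needs no new data, no contact with families and no change to care. The drawback is that an imbalance could reflect coding rather than reactions, and the board should be told so.

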12.2 Definitions

12.2.1 Adverse Event (AE)

Not applicable to this study.

12.2.1.1 Suspected Adverse Reaction (SAR)

Not applicable.

12.2.2 Unexpected Adverse Event

Not applicable.

12.2.3 Serious Adverse Event (SAE)

Not applicable.

12.3 Grading and Attribution of Adverse Events

12.3.1 Grading Criteria

Not applicable.

Table 12.3.1. Grading of Adverse Events Related to Exposure to Peanut-Containing Foods

Not applicable.

12.3.2 Attribution Definitions

Not applicable.

Table 12.3.2 Attribution of Adverse Events

Not applicable.

12.4 Collection and Recording of Adverse Events

12.4.1 Collection Period

Not applicable.

12.4.2 Collecting Adverse Events

Not applicable

12.4.3 Recording Adverse Events

Not applicable.

12.5 Reporting of Serious Adverse Events and Adverse Events

12.5.1 Reporting of Serious Adverse Events to Sponsor (*[DAIT/NIAID or other Sponsor, if applicable]*)

Not applicable.

12.5.2 Reporting to Health Authority

Not applicable: This study, which does not involve an investigational product or device, is not regulated by a Health Authority.

12.5.2.1 Annual Reporting

Not applicable.

12.5.2.2 Expedited Safety Reporting

Not applicable.

12.5.3 Reporting of Adverse Events to IRBs/IECs

Not applicable.

12.6 Pregnancy Reporting

Not applicable.

12.7 Reporting of Other Safety Information

The study Principal Investigator shall promptly notify the SACCC, DAIT/NIAID, and the IRBs when an “unanticipated problem involving risks to subjects or others” is identified, which is not otherwise reportable as an adverse event. The Office for Human Research Protections considers unanticipated problems, in general, to include any incident, experience, or outcome that meets all of the following criteria:

Unexpected (in terms of nature, severity, or frequency) given (a) the research procedures that are described in the protocol-related documents, such as the IRB-approved research protocol and informed consent document; and (b) the characteristics of the subject population being studied;

Related or possibly related to participation in the research (in this guidance document, possibly related means there is a reasonable possibility that the incident, experience, or outcome may have been caused by the procedures involved in the research); and

Suggests that the research places subjects or others at a greater risk of harm (including physical, psychological, economic, or social harm) than was previously known or recognized.

12.8 Review of Safety Information

12.8.1 Medical Monitor Review

The DAIT/NIAID Medical Monitor shall receive periodic reports, at a frequency determined by DAIT/NIAID, from the study's Data Center compiling new and accumulating information on unanticipated problems. In addition, the Medical Monitor shall review and make decisions on the disposition of such problems.

12.8.2 DSMB Review

12.8.2.1 Planned DSMB Reviews

The Data and Safety Monitoring Board (DSMB) shall review the progress of the study and any available safety information at least yearly during planned DSMB Data Review Meetings. Data for the planned safety reviews will include, at a minimum, a listing of all reported unanticipated problems.

12.8.2.2 *Ad hoc* DSMB Reviews

In addition to the pre-scheduled data reviews, the DSMB may be called upon for ad hoc reviews. The DSMB will review any event that potentially impacts safety at the request of the Principal Investigator or DAIT/NIAID. After review of the data, the DSMB will make recommendations regarding study conduct and/or continuation.

12.8.2.2.1 Temporary Study Suspension of <enrollment/drug dosing or both> for *ad hoc* DSMB Safety Review

If an *ad hoc* safety review is triggered, the DAIT/NIAID will decide whether any aspects of the study should be temporarily suspended before an *ad hoc* DSMB review.

13. Statistical Considerations and Analytical Plan

13.1 Overview

Analysis of study data will be conducted to address all study objectives and to understand other interrelationships among all data elements of interest to the investigators and of relevance to the objectives of the study. Although the study has recruited 37 practice sites prior to protocol initiation, the analytical plan is based on 30 practice sites as a conservative estimate due to potential attrition.

13.2 Endpoints

Primary Endpoints:

- % of infants at *low risk for peanut allergy* whose pediatric clinician adhered to the guidelines for that infant.
- % of infants at *high risk for peanut allergy* whose pediatric clinician adhered to the guidelines for that infant.

Secondary Endpoint:

- % of infants at *low risk for peanut allergy* who developed peanut allergy by age 2.5.
- % of infants at *high risk for peanut allergy* who developed peanut allergy by age 2.5.

Exploratory Endpoint 1:

- % of infants at *high risk for peanut allergy* whose allergist adhered to the guidelines.

Exploratory Endpoint 2: Pediatric clinician and caregiver reported knowledge, attitudes, and barriers and facilitators to PPA Guideline adherence.

Exploratory Endpoint 3: Each of the following endpoints include infants that are fully adherent and those that are adherent despite conflict with the clinician recommendation as defined in Figure 6. The endpoints for high risk infants can only be determined for infants where clinician testing (e.g. IgE and/or skin prick tests) is available in order to determine guideline consistent caregiver behavior.

- % of infants at *low risk for peanut allergy* whose caregiver introduced peanut by 12 months of age.

- % of infants at *high risk for peanut allergy* whose caregiver introduces peanut products by 7 months of age and continues feedings with at least 6 g of peanut protein over ≥ 3 feedings per week as reported around the infant's 1st birthday in accordance with the peanut allergy prevention guidelines.% of infants at *high risk for peanut allergy* whose caregiver introduces peanut products but does not do so by 7 months of age or does not continue feedings with at least 6 g of peanut protein or over ≥ 3 feedings per week as reported around the infant's 1st birthday. 13.3 Measures to Minimize Bias

A minimum of 30 participating clinic sites will be randomized in a 1:1 ratio to the intervention arm (i.e., offering iREACH intervention) or standard care (i.e. without iREACH). Using a computerized random number generator, the randomization will be stratified by practice site size to achieve balanced allocation of participants into the intervention and standard care arms. This process will be performed by the Lurie DCC biostatistician, who is blinded to the intervention delivery and will not be aware of the identity of participating sites.

